## 8 Schedule of Subject Activities

### 8.1 Visit 1: Screening and Baseline

#### 8.1.1 Screening

A Pre-screening Log will show 1) all patients (anonymized) who presented with an impending pathological fracture or actual fracture but who were not offered the study and the reason(s) and 2) all patients to whom the study was described but who declined participation.

Qualified patients who agree to participate in the study will be required to sign an informed consent form (ICF). After signing the ICF, study subjects will undergo study-specific screening procedures.

All patients who consent to the study will be listed on the Screening/Enrollment Log. This log will document the date of screening, the results of screening, and the primary reason for exclusion if the subject did not satisfy the initial eligibility criteria or was disqualified during surgery.

### **8.1.2 Baseline**

The following will be performed after the subject has signed an ICF:

A clinical assessment will be performed as follows:

- Inclusion and exclusion criteria review;
- Relevant medical history, including smoking history, osteoporosis history, work status, and whether the patient has any disabilities, with a focus on the impending fracture site;
- Physical exam, with focus on target limb, including neurovascular exam, including radiographic assessment and Mirels scoring of the impending pathological fracture;
- Urine pregnancy test (if applicable);
- Current concomitant pain medication use;
- Patient-completed pain VAS;
- Standard of care radiographs of target impending or actual fracture prior to signing consent form;
- MSTS Functional Score and EORTC QLQ-BM22; and
- Optional health economics assessments.

The procedures required for Screening and Baseline may be conducted during more than one visit, provided that all procedures are conducted prior to index treatment.

### **8.2 Visit 2: Surgery and Post-index Procedures/Discharge**

At the time of surgery, should the surgeon discover the presence of a condition that would render the subject ineligible for study participation, the subject will not be treated with the IlluminOss device. The subject should receive the standard of care as determined by the surgeon.

The Instructions for Use (IFU) outlines the full procedure for implantation of the IlluminOss device, along with the device preparation guidance.

Non-medical sponsor representatives and/or designees may be present during the procedure to provide technical assistance to the investigator.

If a bone defect exists, this defect must be measured to confirm eligibility prior to insertion of the IlluminOss PBSS.

*Note: The use of materials to promote bone fusion (i.e., bone graft, bone growth stimulators, etc.) during the index procedure is prohibited.*

The following information will be collected during Visit 2:

- Date of surgery;
- Duration of procedure;

- Fracture treatment information (including IlluminOss device lot number and size of device used);
- AE assessment;
- Use of pain medications;
- Physical therapy prescription(s);
- Return to pre-fracture mobility;
- Date of discharge.

*Note: If placement of the IlluminOss PBSS is attempted but not successful, the subject will receive the standard of care as determined by the surgeon. This subject will still be part of the ITT population and followed for safety.*

If available, health economic data may be obtained. The subject's billing information relating to the surgical procedure (i.e., operating room time, length of stay, medications), follow-up visits, rehabilitation, and other related procedural costs may be collected.

### **Post-index Procedure Clinical Considerations**

Standardized post-operative management will be conducted for all subjects. The post-operative management schema is found in Appendix 13.3.

*Note: Bone growth stimulators (biological, electrical, ultrasound, or magnetic) are prohibited.*

Visits 1 and 2 may occur during the same day if acute stabilization of the impending fracture is required. This is at the discretion of the PI. It should be noted that obtaining informed consent should always be done prior to performing any study-specific procedures.

### **8.3 Follow-up Visits and Evaluations**

Follow-up evaluations will be scheduled for 7-14, 30, 90 days post-index procedure and the extended follow up at 180 and 360 days post-index procedure.

#### **8.3.1 Visit 3: 7-14 day Follow-up (+ 3 days)**

The following will be performed:

- AE assessment;
- Concomitant/pain medications;
- Subject-completed pain VAS;
- MSTS Functional Score and EORTC QLQ BM22;
- Clinical assessments that include, but are not limited to, assessments for pain, return to baseline mobility, range of motion, return to work, disability status, use of pain medication, and physical therapy prescription status; and
- Radiographs of treatment site (A/P and Lateral)

If available, additional health economic data may be obtained.

### **8.3.2 Visit 4 and 5: 30-day Follow-up ( $\pm$ 7 days) and 90-day Follow-up ( $\pm$ 14 days)**

The following will be performed:

- AE assessment;
- Concomitant/pain medications;
- Subject-completed pain VAS;
- MSTS Functional Score and EORTC QLQ BM22;
- Clinical assessments that include, but are not limited to, assessments for pain, return to baseline mobility, range of motion, return to work, disability status, use of pain medication and physical therapy prescription status; and
- Radiographs of treatment site (A/P and Lateral)

If available, health economic data may be obtained.

### **8.3.3 Extended Follow Up Visits 6 & 7: 180-day Follow-up ( $\pm$ 30 days) and 360-day Follow-up ( $\pm$ 30 days)**

The following will be performed:

- AE assessment;
- Concomitant/pain medications;
- Subject-completed pain VAS;
- MSTS Functional Score and EORTC QLQ BM22;
- Clinical assessments that include, but are not limited to, assessments for pain, return to baseline mobility, range of motion, return to work, disability status, use of pain medication and physical therapy prescription status; and
- Radiographs of treatment site (A/P and Lateral)

If available, health economic data may be obtained.

## **8.4 Activities Performed by Sponsor Representatives**

One or more non-medical representatives of the sponsor may be present during implantation of the device.

## **9 Adverse Events, Adverse Device Effects and Device Deficiencies**

### **9.1 Definitions**

Adverse Event (AE): any untoward medical occurrence, unintended disease or injury or untoward clinical signs (including abnormal laboratory findings) in patients, users or other persons, whether it is considered device related or not. Only adverse events which are new or have worsened will be evaluated in the safety assessment.

The severity of the AE should be assessed based on the following definitions:

- Mild: an AE that is noticeable to the patient and may require additional therapy;
- Moderate: an AE that interferes with the patient's activities and requires intervention or additional therapies;
- Severe: an AE that is intolerable, or necessitates additional therapy, or places the patient at immediate risk of harm.

Serious Adverse Event: An AE is considered serious (SAE) if it

- results in death,
- led to serious deterioration in health that either:
  - resulted in life-threatening illness or injury, or
  - required in-patient hospitalization or prolongation of existing hospitalization, or
  - resulted in a permanent impairment of a body structure or a body function, or
  - Resulted in medical or surgical intervention to prevent life threatening illness, or
  - led to fetal distress, fetal death or a congenital abnormality or birth defect.

Note that planned hospitalization for a pre-existing condition or a procedure required by the protocol, without serious deterioration in health, is not considered an SAE.

Device Deficiency: A device deficiency is defined as inadequacy of a medical device with respect to its identity, quality, durability, reliability, safety, or performance.

Unanticipated Adverse Device Effect (UADE): an AE is considered to be a UADE if there is an occurrence of an adverse effect on health or safety, if that effect or problem was not previously identified in nature, severity, or degree of incidence in the investigational plan or application, or if any other unanticipated problem associated with the device occurs that relates to the rights, safety or welfare of patients.

Device-related AE: an AE is considered to be device-related when, in the judgment of the PI, the clinical event has a reasonable time sequence associated with use of the investigational device and is unlikely to be attributed to concurrent disease or other procedures or medications. It is reasonable to believe that the device directly caused or contributed to the AE.

Procedure-related AE: an AE is considered to be procedure-related when, in the judgment of the PI, it is reasonable to believe that the event is associated with the device implant or removal procedures and is not specific to the investigational device used. Other products, surgical techniques, or medications required specifically for the procedure are likely to have contributed to the occurrence of the event.

For purposes of this study, the following events are not considered to be AEs because they are normally expected to occur in conjunction with the device-implant and/or removal procedures, or are associated with customary, standard care of patients undergoing surgical procedures for treatment of arm fractures:

- Early post-operative pain (within 72 hours post-index procedure) at the access site and/or related to position on procedure table;
- Post-anesthesia/conscious sedation emesis, nausea, or headache (within 24 hours post-index

procedure);

- Electrolyte imbalance without clinical sequelae following index procedure, even if requiring correction;
- Systolic or diastolic blood pressure changes that do not meet the definition of hypotension or hypertension;
- Low grade temperature increase ( $\leq 38.3^{\circ}\text{C} / \leq 101^{\circ}\text{F}$ ) within 24 hours of index procedure;
- Hematocrit decrease from baseline, but not associated with hemodynamic changes and remaining above 30%;
- Blood loss without transfusion, associated with a decrease in hemoglobin or hematocrit of  $< 2$  g/dl or  $< 6\%$ , respectively from baseline level with a resulting hematocrit that is  $\geq 30\%$  (or hemoglobin  $\geq 10$  g/dl);
- Minor, localized tenderness, swelling, induration, oozing, etc. at the surgical site.

This listing of events is intended to provide guidance to the investigational sites for purposes of AE reporting. The PI at the investigational site should utilize his/her own clinical judgment in evaluating subject AEs, and may determine that the above events should be reported as AEs.

The PI should follow all unresolved SAEs until the events are resolved or the investigator assesses them as chronic or stable, the subject is lost to follow-up, the subject has withdrawn consent, or the AE is otherwise explained.

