#### **7.8.9 Adverse Events**

Adverse events (AEs) will be coded by System Organ Class (SOC) and Preferred Term (PT) using the Medical Dictionary for Regulatory Activities (MedDRA). Incidences of treatment-emergent AEs (TEAEs) will be presented. Incidences of TEAEs will also be presented by maximum severity, seriousness, and relatedness (device or procedure related) at Day 90 and during the extended follow up visits. This includes the reporting of device revisions, reoperations, removals, supplemental fixations, or other procedures.

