6.7.1.2 Adverse Events (AEs)

Adverse events (AEs) will be collected from the time of surgery until the last study visit or premature discontinuation from the study.

Treatment-emergent adverse events (TEAEs) are those AEs which worsen in severity on or after date of surgery or with onset date on or after date of surgery. AEs with missing start dates, but with stop dates either overlapping into the treatment period or missing, will be considered TEAEs. Treatment-related includes possibly or probably or definitely relationship of the event to the investigational device, procedure, anesthesia, or oncology medicine.

All AEs will be coded by System Organ Class (SOC) and Preferred Term (PT) using the Medical Dictionary for Regulatory Activities (MedDRA). Incidences of TEAEs will be tabulated by SOC and PT, cumulatively per time point (Up to Day 90, Up to Day 180, and Up to Day 360). Incidences of TEAEs will also be presented by maximum severity, seriousness, unanticipated adverse device effect (UADE) and relatedness (device or procedure related) cumulatively per time point. This includes the reporting of device revisions, reoperations, removals, supplemental fixations, or other procedures. Subjects who discontinued due to TEAEs will be summarized by SOC and PT in a separate table. Patients are counted only once in each SOC, and only once in each PT category, cumulatively per time point.

The following tables will be developed for summarizing AEs cumulatively per time point.

- Overall summary of TEAEs, it includes number of treatment-emergent adverse events, subjects with any TEAE, subjects with any serious adverse events (SAE), subjects with any severe TEAEs, subjects with any device related TEAEs, subjects with any procedure related TEAEs, subjects with any anesthesia related TEAEs, subjects with any Oncology Medicine related TEAEs, subjects with any unanticipated adverse device effect (UADE), subjects with TEAEs leading to study discontinuation and death.
- Summary of TEAEs by system organ class and preferred terms
- Summary of serious TEAEs by system organ class and preferred terms
- Summary of TEAEs by system organ class, preferred terms and maximum severity

- Summary of treatment-related TEAEs by system organ class, preferred terms (device related, procedure related, anesthesia related and oncology medicine related).
- Summary of unanticipated adverse device effect (UADE) by system organ class and preferred terms

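### The adverse-event severity grades overlap for events that need additional therapy, so the severity tables cannot separate grades among those events

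*Protocol*

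**What the plan says.** Protocol section 9.1 introduces the scale with an instruction: "The severity of the AE should be assessed based on the following definitions". The three grades are:

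- The lowest grade, Mild, covers an event that the patient notices, with additional therapy permitted but not required.
- The middle grade, Moderate, covers an event that gets in the way of what the patient does and that also "requires intervention or additional therapies".
- The highest grade is a list of alternatives, any one of which is enough: "Severe: an AE that is intolerable, or necessitates additional therapy, or places the patient at immediate risk of harm".

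Neither the protocol nor the SAP gives a rule for an event that fits two grades, and the SAP does not redefine severity. Its only severity rule, in section 7.0, is that an AE with no recorded severity is counted as severe.

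The grade is used in these places:

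- Protocol section 7.8.9 plans treatment-emergent AE (TEAE) incidence by maximum severity.
- SAP section 6.7.1.2 lists a "Summary of TEAEs by system organ class, preferred terms and maximum severity" and, in the overall summary, "subjects with any severe TEAEs". Both are cumulative to Days 90, 180 and 360.
- Protocol section 4.5 has medical monitoring look at AE severity along with frequency and relatedness.

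**The concern.** A severity scale works if each event falls into one grade. Here the need for additional therapy appears in all three definitions, and in the highest it is sufficient by itself. A tolerable event that the patient notices and that is treated with one extra medication fits both Mild and Severe. If it also interferes with activities, it fits all three. Two investigators who both follow the text can therefore put the same event at opposite ends of the scale.

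The protocol's own glossary supplies a case. Section 13.1 defines general discomfort as needing minor treatment, such as aspirin, or none. If the aspirin counts as additional therapy, that event meets the Severe definition.

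At stake is the meaning of the severe-event count. Safety is part of the primary objective, and the study has no concurrent arm to show whether a high or low count comes from how the scale was read. With 80 subjects at up to 20 sites, the average could be as low as 80 / 20 = 4 subjects per site, so differences between sites in reading need not average out.

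**Working it through.** The plan gives no figure to reproduce, and the documents give no expected AE rates. The check is therefore logical.

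**Inputs (Protocol section 9.1).** Describe an event by six yes/no attributes: noticeable (N), interferes with activities (A), needs additional therapy (T), needs another intervention (I), intolerable (X), immediate risk of harm (R). That gives 2^6 = 64 combinations. They show which grades can coincide; they are not event frequencies.

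**Rules as written.**

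- Mild: N. Therapy is permitted, so T does not restrict it.
- Moderate: A and (I or T).
- Severe: X or T or R.

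**Events that need additional therapy (T = yes).** There are 32 combinations, and all 32 meet Severe: 8 meet Severe only, 8 Mild and Severe, 8 Moderate and Severe, and 8 all three. So 24 of the 32 also meet a lower grade.

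**The same events when neither intolerable nor an immediate risk.** There are 8 combinations. All 8 still meet Severe through therapy alone, and 6 of the 8 also meet Mild, Moderate or both.

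**Overlap of Moderate with Severe.** Moderate is met in 32 x 3/4 = 24 combinations, and 22 of these also meet Severe. The other 2 need an intervention but no additional therapy.

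**Would a highest-grade rule alone be enough?** No. Severe would take 64 x 7/8 = 56 combinations, Moderate 2 and Mild 3, and 3 would meet no grade (56 + 2 + 3 + 3 = 64). Moderate would be nearly empty. The SAP's maximum severity is in any case a maximum over recorded grades; it does not say how to grade one event.

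**Would deleting the therapy condition alone be enough?** No. The two combinations with T = yes and N, A, X and R all no would lose their only grade, so ungraded combinations would rise from 3 to 3 + 2 = 5. This case is realistic: section 9.1 counts abnormal laboratory findings as AEs, and a patient may not notice one that is treated. If such a grade were left blank, SAP section 7.0 would count it as severe.

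**With the rules under the fix.** Severe is X or R: 64 x 3/4 = 48. Of the remaining 16, Moderate is A and (I or T): 2 x 3 = 6. Mild is everything else: 16 - 6 = 10. The total is 48 + 6 + 10 = 64, with one grade per combination.

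**The case against.** The strongest reply is that little depends on the grade. The tables are descriptive. The hypothesis tests concern VAS and MSTS. Safety Success (SAP section 6.7.1.1) rests on device-related serious AEs, reoperation pages and recorded device malfunction. Seriousness has its own definition, and expedited reporting (Protocol section 9.3) follows seriousness, unanticipated device effects or death. With one arm, no between-group comparison of severity can be distorted. All of this stands, and it limits the point to the severity tables and the severe-event count.

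A second reply is that investigators will grade by judgement. The judgement sentence in section 9.1 concerns whether certain expected events are reported as AEs at all; it gives no rule for choosing a grade. Actual practice is unknown, though. The annotated CRF is not among the documents and may carry guidance, so divergence between sites is a possibility and has not been shown.

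A reader might infer that the planned tables do not measure severity at all. The text does not support that. An event that needs no additional therapy, is tolerable and poses no immediate risk does not meet Severe, and the scale keeps an ordered core from noticeable, through interference with activities, to intolerable or dangerous. Nor is every treated AE Severe: Moderate names intervention separately from therapy, and an event managed by intervention alone need not reach Severe.

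**Conclusion.** The definitions are wrong as written for AEs that need additional therapy. On a literal reading all such events qualify as Severe, most combinations also qualify for a lower grade, and nothing in either document resolves the conflict. The maximum-severity tables and the count of subjects with any severe TEAE therefore cannot separate grades among those events. The logical result needs no assumption beyond taking the Severe conditions as alternatives, which is how they are joined.

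The numerical size of the effect on the severe count cannot be stated, because the documents give no rate of AEs needing therapy and no rate of intolerable or dangerous AEs. The primary tests, serious AE reporting and Safety Success are unaffected. The rule that counts missing severity as severe is separate from the overlap and matters here only if an event is left without a grade. The correction is worth making because it is cheap and the severe count is otherwise hard to interpret.

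**What to change.** Make the grades mutually exclusive and exhaustive in Protocol section 9.1 and the CRF guidance:

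1. Remove the need for additional therapy as a stand-alone condition for Severe, leaving intolerability and immediate risk of harm.
2. State that when an event meets more than one grade, the highest grade met applies.
3. State that an AE meeting neither the Moderate nor the Severe criteria is Mild, including findings that the patient does not notice.

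Apply the clarified scale to all AEs already graded, upward and downward. Reopening only those entered as Severe would move the count mainly one way in an open-label study. It may also be unworkable, because the AE report items listed in Protocol section 9.5 do not include the reason for a grade.

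The cost is a short wording change, which under Protocol section 10.9 needs sponsor authorization and IRB and FDA approval, plus queries on AE grades. No SAP table, endpoint or sample size changes.

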## **9.3 Reporting to Sponsor**

All AEs classified as SAEs, or UADEs shall be reported by the PI (or designee) to the study CRO via [contact] or email ([contact]) within 24 hours of learning of the AE.

The PI (or designee) shall send a written report, including a narrative description of the SAE/UADE, to the Sponsor or CRO, within 3 working days of the initial report.

Subject death during the study must be reported by the PI (or designee) with written documentation by facsimile to the Sponsor or CRO within 24 hours of the PI's knowledge of the death. Notification of death must include a brief statement of the relevant details of the death and is required to be signed by the investigator. A copy of the death records, death certificates, and an autopsy report (if performed) should be sent to the Sponsor or the Sponsor's authorized representative (CRO) within 10 days post-autopsy.

In the event of death, efforts should be made to perform an autopsy in order to assess the state of the target arm. If autopsy is not performed, written documentation from the PI will be required regarding the reasons why.

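### The first limb of the UADE definition states no link to the device, so an unrelated adverse event not identified in the plan or application can be counted and reported as an unanticipated device effect

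*Protocol*

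**What the plan says.** Protocol 9.1 defines the UADE in one sentence with two limbs.

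- **First limb:** an AE qualifies on this condition: "if there is an occurrence of an adverse effect on health or safety, if that effect or problem was not previously identified in nature".
- **First limb, the comparison:** severity and incidence count as well as nature, and the reference is the investigational plan or the application.
- **Second limb, the alternative:** "or if any other unanticipated problem associated with the device occurs that relates to the rights, safety or welfare of patients".

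The same section defines the base term, AE, to include an event "whether it is considered device related or not". It also defines a device-related AE separately. That definition has a causal test: among other things, the event "is unlikely to be attributed to concurrent disease or other procedures or medications". The UADE sentence does not refer to it.

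Three consequences follow from the label:

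- Protocol 9.3: "All AEs classified as SAEs, or UADEs shall be reported by the PI (or designee) to the study CRO" within 24 hours of learning of the event, with a written narrative within 3 working days.
- Protocol 9.4: UADEs go to the IRB and FDA as the regulations require.
- SAP 6.7.1.2: UADEs have a line in the overall TEAE summary and a table of their own by system organ class and preferred term. The SAP gives no definition, so the protocol's applies.

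**The concern.** A count of unanticipated device effects is read as a statement about the device. The protocol reads it that way itself: Section 3.2 reports the absence of such effects in the EU registry as evidence on device safety. If the working definition does not require a connection with the device, a count from this trial cannot be read in that sense.

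The population makes this a practical matter. Subjects have metastatic cancer and are followed to Day 360. Protocol 9.5 has all AEs recorded regardless of relationship, and SAP 6.7.1.2 provides a relatedness category for oncology medicine, so events from cancer drugs are expected in the data. A site that applies the sentence as written and a site that applies its evident purpose could classify the same event differently, and different reporting duties would follow.

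**Working it through.** There is no figure to reproduce, so the check sets the clauses side by side.

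1. **Does the first limb contain a device link?** No. It needs an adverse effect on health or safety, and it needs that effect not to have been identified beforehand. Neither part mentions the device.

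2. **Does the second limb supply one?** Only for itself. It is joined to the first by an *or*, so an event that meets the first limb never has to meet the second.

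3. **Does the base term supply one?** No. The AE definition expressly takes in events unrelated to the device.

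4. **Does another section supply one?** The device-related AE definition in 9.1 and the relatedness levels in 9.2 could do so, but the UADE sentence does not refer to them. Protocol 9.3 to 9.6 and SAP 6.7.1.2 add no such condition.

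5. **What counts as previously identified?** The comparator is the investigational plan or the application. Within the plan, Section 4.2 lists risks of the device, of humerus surgery and of anesthesia. Appendix 13.1 defines many general events, among them sepsis, pneumonia, pulmonary embolism, urinary tract infection, acute renal failure, anemia, nausea and death. Neither list sets out cancer-drug toxicities as such. The application is not among the documents.

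6. **Test case.** Take mild diarrhea that the investigator attributes to an oncology drug and judges not related to the device. Neither Section 4.2 nor Appendix 13.1 names it. If the application does not identify it either, it meets both parts of the first limb and is a UADE as written. A named event can also qualify, if its severity or incidence goes beyond what was identified.

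7. **Effect on the tables.** The SAP's overall summary counts subjects with any device-related TEAE and subjects with any UADE. Under a definition with a device link, each UADE would carry a device association. Under the present wording the test case adds a subject to the UADE line and none to the device-related line, so the two lines can disagree.

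**The case against.** The strongest reply is that the device link is already in the sentence. The term is an adverse *device* effect, and the second limb speaks of any *other* problem associated with the device, which presupposes that the first limb concerns such a problem too. This stands as evidence of intent, and many investigators will read it so. It does not put the condition into the operative text of a rule that sets reporting duties.

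A second reply is that the error is towards over-reporting and does little harm. Every AE gets a relatedness judgment, and device-related TEAEs are tabulated separately, so a true device signal remains visible there. This also stands, and it limits the point to the meaning of the UADE count and the reporting it triggers.

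A reader might infer more than the documents support:

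- **That every AE missing from the risk list is a UADE.** The comparator includes the application, which is not available here, and Appendix 13.1 names many events common in cancer patients.
- **That a UADE must also be serious and that the definition wrongly omits this.** Nothing in the documents says so. Protocol 9.3 to 9.5 name serious and unanticipated events as separate grounds. If every UADE had to be serious, the separate mention would add nothing to the 24-hour rule. The Revision History says that AE terminology was aligned with the CFR, but the regulation's text is not reproduced.
- **That the UADE count is a main safety result.** It is one line of a summary and one of several AE tables. Safety Success in SAP 6.7.1.1 is built from device-related SAEs, reoperations and device malfunctions, and does not use it.

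**Conclusion.** The point holds as a misworded rule. As written, the first limb admits AEs unrelated to the device that were not identified in nature, severity or incidence in the plan or application. Those events would be reported within 24 hours, sent to the IRB and FDA, and counted in two SAP summaries under a device-effect label.

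The size cannot be stated. The documents give no AE rates, and what counts as identified depends partly on the application. Any distortion is confined to the UADE summaries and the reporting triggered by the label. The VAS and MSTS tests and the Safety Success proportions do not change.

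The conclusion assumes that neither the application nor the CRF instructions, which are not among the documents, adds the missing condition. If one does, the protocol sentence still needs to agree with it.

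**What to change.** In Protocol 9.1, state in the first limb that the adverse effect must be caused by or associated with the device, and leave the second limb as it is. Say how that link is judged, consistently with 9.1 and 9.2. This needs care because the device-related AE definition in 9.1 and the possibly-related level in 9.2 do not draw the line in the same place, and the levels in 9.2 cover device and procedure together. SAP 6.7.1.2 already counts possibly, probably and definitely related events as treatment-related, so the sponsor should state which levels satisfy the UADE condition.

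In SAP 6.7.1.2, refer to the same definition for both UADE summaries.

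On seriousness, the sponsor should reconcile the UADE definition with the SAE definition and with the regulation it follows, and state the answer explicitly.

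The cost is one sentence in the protocol, a cross-reference in the SAP, and matching CRF guidance. The downside is that fewer events will carry the UADE label. SAEs remain reportable within 24 hours whatever their cause, and all AEs are still recorded with a relatedness judgment.
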